7.4 Compliance with study intervention

Compliance is of uttermost importance in this project. To improve adherence to the intervention, participants are contacted by phone once a week by the study personnel. Apart from answering upcoming questions this allows the study personnel to remind the participant to take the sweeteners regularly, to fill in the questionnaires and to come to the appointments. At the end of the study, the return of unused portions will allow us to estimated compliance. Non-compliance: In case a participant does not take the sweeteners as planned, or fails to fill in the forms and come to the appointments the participant has to be excluded.

7.5 Data Collection and Follow-up for withdrawn participants

In case a participant wishes to discontinue study participation, the data collected to this time point is included in the analysis. A follow-up visit is not planned in this case.

7.6 Trial specific preventive measures

Concomitant medication with an antibiotic might impact findings in vascular assessment and needs to be reported to the study personnel.

7.7 Return or Destruction of sweeteners

The returned sweetener portions are counted and destroyed.

8. STUDY ASSESSMENTS

8.1 Study flow chart(s) / table of study procedures and assessments

See: STUDY SCHEDULE

8.2 Assessments of outcomes

8.2.1 Assessment of primary outcome

Oral glucose tolerance test (OGTT):

At baseline and after the treatment period (ca. 49d plus 3 days) an oral glucose tolerance test is carried out.

Patients are instructed:

- that they should not have been acutely ill (acute infection of any kind) within 14 days prior to OGTT.
- to abstain from strenuous exercise within the last 48h before OGTT,
- to make sure their main meals within the last 48h before OGTT include carbohydrates,
- that they must not eat or drink, nor consume alcohol or smoke within 10 hours before OGTT.

Blood sampling: After an overnight fast of at least 10 hours an antecubital catheter will be inserted into a forearm vein for blood collection. After a fasting blood sample on ice into 7.5mL tubes containing EDTA (6 µmol/L) the participant will ingest a 75g glucose solution (300 ml OGTT syrup, Roche) within 5-10min.

Further blood samples will be taken at regular time intervals (30, 60, 90, and 120 min).

Tubes will be centrifuged at 4° C at 3000 rpm for 10 min and 4 plasma sample aliquots are pipetted into 1.5mL tubes (aliquots à 600μ L plasma each; tubes labelled: ① Insulin/Glucose, ② C-Peptide, ③ Reserve 1, ④ Reserve 2). Samples will be stored at -80° C until analysis of plasma glucose, insulin and C-peptide.

STANDARD ORAL GLUCOSE TOLERANCE TEST: DEFINITIONS

Diabetes Fasting plasma glucose ≥7.0mmol/l or ≥11.1mmol/l (OGGT: 2–h plasma glucose))

Impaired Glucose Tolerance (IGT) Fasting plasma glucose <7.0mmol/l and ≥7.8 and <11.1mmol/l (OGGT: 2-h plasma glucose)

Impaired Fasting Glucose (IFG) Fasting plasma glucose 6.1 to 6.9mmol/l and <7.8mmol/l (OGGT: 2-h plasma glucose)

- > OGTT: venous plasma glucose 2-h after ingestion of 75g oral glucose load

Definition and Diagnosis of Diabetes Mellitus and Intermediate Hyperglycaemia: Report of a WHO/IDF consultation. World Health Organization 2006

8.2.2 Assessment of secondary outcomes

Faecal samples for human gut microbiota composition and metabolomics:

- Patients will get 2 faeces containers (107x25mm, Sarstedt, Ref. 80.622.111) for faecal sampling.
- One container will be used for gut microbiota analysis and one for metabolomics.
- Patients are instructed to pass the specimen (stool) onto a plastic wrap or disposable plate (at home) and to take ca. four pea-sized (or bigger) amounts of stool material for each plastic container using the spatula attached to its cap. Sampling needs to be from the internal side of the faeces (not just a swab of the surface).
- Patients will keep the sample in the fridge at 4°C and bring them to St. Claraspital hospital within 24 hours, where the sample will be stored at -80°C until analysis.

 **Analyses:*
- The taxonomic and functional profiles of the gut microbiota will be assessed by metagenomic shotgun sequencing.
- Faecal samples will be used for analysis of the metabolome using metabolomics (using 1H-NMR 600mHz at UCL).²²

Urine sample for metabolomics:

- The urine sample is freshly obtained (at our outpatient clinic, metabolic visit 1 and 2: after an overnight fast of 10 hours, but not necessarily first void in the morning).
- Patients receive a common urine container (as used in hospital) and are instructed to deliver midstream urine.

- From the freshly obtained urine, four aliquots of 1mL each are pipetted into Eppendorf's safe lock 2mL tubes and are frozen and stored at -80°C until analysis.
- In case direct processing is impossible, urine is kept in the fridge at 4°C for a maximum of 1 hour and then aliquoted and frozen.

Analyses:

 The urine samples will be used for analysis of the metabolome using metabolomics (using 1H-NMR 600mHz at UCL).²²

Blood lipid profile, hepatic enzymes and hsCRP:

Fasting samples will be taken to measure triglyceride, total cholesterol, LDL (low-density lipoprotein) and HDL (high-density lipoprotein) levels, the liver enzymes ASAT (aspartate transaminase) and ALAT (alanine transaminase) and hsCRP (high-sensitive C-reactive protein) at baseline an after the treatment period. Analysis will be carried out in the hospital laboratory (St. Claraspital).

Reference values:

ASAT and ALAT: < 35 U/L in females and < 50 U/L in males

Triglycerides: < 2.0 mmol/L
Total cholesterol: < 5.2 mmol/L
LDL: < 2.6 mmol/L
HDL: > 1.6 mmol/L
hsCRP: < 5 mg/L

Experimental blood analysis:

For measurement of inflammatory response (IL-6, TNF- α , sTNFR1, sTNFR2), and intestinal permeability (zonulin, LPS), a fasting blood sample will be taken at baseline and after the treatment period.

Blood sampling: After an overnight fast of at least 10 hours, an antecubital catheter will be inserted into a forearm vein for blood collection. Venous blood samples are drawn into a sterile, pyrogen-free 7.5mL collection tube containing a clot activator and gel for serum separation and then centrifuged at 3000 rpm for 10 min at 4°C. In addition, for LPS, pyrogen free heparin citrate tubes are used in venipuncture.

Aliquots: Six serum aliquots (containing 600μL serum each; labelled ① IL-6, ② TNF- α , ③ sTNFR1, ④ sTNFR2, ⑤ Zonulin ⑥ Reserve experimental) are pipetted with pyrogen-free tips into 6x1.5-ml pyrogen-free tubes and frozen at -80° C until further analysis. In addition, two serum aliquots (containing 250μL serum each; labelled ① LPS-1, ② LPS-2) are pipetted with pyrogen-free tips into 2x1.0-ml pyrogen-free tubes and frozen at -80° C until further analysis.

Inflammatory response

- High sensitive CRP (hsCRP) is measured in the hospital laboratory (St. Claraspital), see above.
- For IL-6 and markers of the tumour necrosis factor α pathway [TNF α , soluble TNF receptor 1 (sTNFR1), and 2 (sTNFR2)] aliquots are stored:

Analyses:

- Serum IL-6 will be measured by a commercially available ELISA kit (EZHIL6; Merck-Millipore)
- **Serum TNF-α** levels will be measured using a commercially available enzyme-linked immunosorbent assay (Invitrogen KHC 3011, U.S.A.). Results are expressed as pg/mL.
- **Serum sTNFR1** levels will be measured using a commercially enzyme-amplified sensitivity immunoassay kit (Invitrogen, KAC 1761, U.S.A.). Results are expressed as ng/mL.
- **Serum sTNFR2** levels will be measured using a commercially enzyme-amplified sensitivity immunoassay kit (Invitrogen, KAC 1771, U.S.A.). Results are expressed as ng/mL.

Intestinal permeability:

- **Serum zonulin** concentrations will be measured by a zonulin ELISA Kit (K5600, Immundiagnostik AG, Bensheim, Germany).
- **LPS** (lipopolysaccharide) concentrations will be measured by LAL (Limulus amebocyte lysate) technique (MCS cartridges Charles River, U.S.A.).

Gastrointestinal tolerance (bloating, diarrhea, reflux):

Gastrointestinal symptoms will be assessed by use of a validated questionnaire (Clinical rating scale for gastrointestinal symptoms: Svedlund et al., 21). The questionnaire will be used at baseline and at the end of week 3 and 7 (self-reporting). A license agreement will be sent to AstraZeneca (ASTRAZENECA AB, 556011-7482 S-151 85 Södertälje, Sweden). The GSRS is a disease-specific instrument, developed based on reviews of gastrointestinal symptoms and clinical experience, to evaluate common symptoms of gastrointestinal disorders. ^{21,23} The GSRS contains 15 items, each rated on a seven-point Likert scale from no discomfort to very severe discomfort. Based on a factor analysis, the 15 GSRS items break down into the following five scales: abdominal pain (abdominal pain, hunger pains and nausea); reflux syndrome (heartburn and acid regurgitation), diarrhoea syndrome (diarrhoea, loose stools and urgent need for defecation), indigestion syndrome (borborygmus, abdominal distension, eructation and increased flatus) and constipation syndrome (constipation, hard stools and feeling of incomplete evacuation).²³ The scores are calculated by taking the mean of the items completed within an individual scale, with higher scores indicating greater severity of symptoms. The GSRS in European patient populations has a good internal consistency reliability and acceptable construct validity and responsiveness.²³⁻²⁵ The GSRS can be administered in either self-report or interview format.

Intestinal Glucoseabsorption: We will assess intestinal glucose absorption by use of a validated technique ^{26,27}. During the oral glucose tolerance test, 3g of 3-O-Methyl-Glucose (3-OMG) is ingested. 3-OMG is then measured in the plasma samples obtained at 0-30-60-90-120min by means of high performance exchange chromatography.

8.2.3 Assessment of other outcomes of interest

Food diary: In order to minimize the confounding factor of possible reduced sugar intake, prior to inclusion nutrition habits will assessed by a questionnaire. Participants will also fill in a food diary during week 3 and 7 (see appendix).

8.2.4 Assessment of safety outcomes

Participants are contacted on a weekly base. However, they will all be provided with a personal phone number of the principal investigator [name] [name] and the study nurse [name] and in case of any undesired effects, participants are to inform the principal investigator directly.

8.2.4.1 Adverse events

Possible adverse events associated with polyol-intake are gastrointestinal symptoms (diarrhoea, bloating), therefore we will assess gastrointestinal symptoms before and during the study by means of a questionnaire (GSRS). In theory an allergic reaction to one of the two substances are also possible. Participants will be asked to report any specific and unspecific symptoms.

8.2.5 Assessments in participants who prematurely stop the study

Participants who discontinue the study are not seen for a follow up visit, as the data obtained after discontinuation will not be useful for our analysis. However, the baseline data will be included in our analyses.

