4.2 Secondary Outcomes

- Human gut microbiota composition: Faecal samples will be taken before and after treatment and the taxonomic and functional profiles of the gut microbiota will be assessed by metagenomic shotgun sequencing.
- Metabolomics: Faecal and urine samples will be used for analysis of the metabolome using metabolomics.
- Blood lipid profile, hsCRP and hepatic enzymes: Fasting samples will be taken to measure triglyceride, total cholesterol, LDL and HDL levels, and the liver enzymes ASAT (aspartate transaminase) and ALAT (alanine transaminase). The analysis will be carried out in the hospital laboratory (St. Claraspital).
- **Inflammatory response:** As erythritol might act as a radical scavenger and reduce oxidative stress, we plan to assess inflammatory state by measuring IL-6, TNF-α, sTNFR1, sTNFR2, high sensitive CRP (hsCRP) and leucocytes.
- Intestinal permeability: Circulating markers of intestinal permeability (zonulin, LPS) will be measured.
- Gastrointestinal tolerance (bloating, diarrhoea etc.): We will assess gastrointestinal symptoms by using a validated questionnaire (Clinical rating scale for gastrointestinal symptoms: Svedlund et al.²¹). The questionnaire will be used at baseline and at the end of week 3 and 7 (self-reporting). A license agreement will be sent to AstraZeneca (ASTRAZENECA AB, 556011-7482 S-151 85 Södertälje, Sweden).
- 4.3 Intestinal Glucoseabsorption: We will assess intestinal glucose absorption by use of a validated technique: during the oral glucose tolerance test, 3g of 3-O-Methyl-Glucose (3-OMG) is ingested. 3-OMG is then measured in the plasma samples obtained at 0-30-60-90-120min. Other Outcomes of Interest

We accept that a possible confounder might be the substitution of sucrose in daily life as polyols might serve as a substitute. If sugar consumption is reduced, metabolic effects could be caused by reduced sugar exposure rather than polyol intake. We will therefore assess overall sugar consumption before and during the trial. Participants will keep a food diary. For this purpose we will use the clinical diary used by our nutritionists for preoperative assessment of bariatric patients.

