4.4 Safety Outcomes

Gastrointestinal tolerance (bloating, diarrhoea etc.): Incidence and severity of gastrointestinal side effects related to the sweetener intake during the study is assessed by using a questionnaire (Clinical rating scale for gastrointestinal symptoms: Svedlund et al.²¹)

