5. STUDY DESIGN

5.1 General study design and justification of design

This pilot trial is a randomized, controlled interventional study; the project set-up will be single-centre, national. Participants will be randomized to one of the three groups: control-group (1), xylitol group (2) or erythritol group (3). They will then get pre-portioned sticks of either xylitol (24g/d; 3x8g) or erythritol (36g/d; 3x12g) or no food supplement (control-group). During the whole period patients will keep a food diary, where they will also report intake of sweeteners and once a week they will fill in a clinical gastrointestinal symptoms questionnaire. The food diary and gastrointestinal symptoms questionnaire will be sent to the clinical trial unit once a week. Once every week volunteers will receive a phone call by the study nurse in order to make sure the sweetener is well-tolerated, compliance is guaranteed and no adverse events occur. At baseline and after 7 weeks, patients will be examined: a) metabolic work-up: oral glucose tolerance test, liver enzymes, blood lipids, b) biomarkers of gastrointestinal permeability and inflammatory response, c) urine and faecal samples (metabolomics), and d) faecal sampling (gut microbiota composition). Upon conclusion of the study, remaining sweetener sticks and questionnaires are returned.

Demographic and personal data (year of birth, weight, height, age, gender, abdominal circumference, blood pressure, medical history) will be saved in a computer database.

Participant recruitment will be achieved through referring physicians from the Ernährungszentrum St. Claraspital, where morbidly obese patients are seen in an outpatient setting before bariatric surgery and are usually on a rather long waiting list before surgery. In case patients are interested in participating,

Effect of the natural sweeteners erythritol and xylitol on vascular function in obese volunteers:

A pilot study, Version 1, 11.4.2016, Version 2, 6.6.2016, Version 3, 25.9.2017

they will be contacted by the principal investigator ([name] [name]) or the study nurse ([name]) and a screening appointment will be made.

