7.3 Dose / Device modifications

In case the participant has forgotten one portion, he/she can take two portions at once without any problems. The participant cannot change the intake schedule and dosage. In case the polyol is not tolerated well (gastrointestinal symptoms), the study has to be discontinued.

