10.4 Planned Analyses

10.4.1 Datasets to be analysed, analysis populations

In this pilot trial which is purely observational, an analysis per protocol is planned. Drop-outs will be replaced, but baseline data of drop-outs might be included to characterize the baseline population. Baseline values of all three groups will be compared, to rule out any baseline differences. The control group will also be examined twice, and the two time-points should yield similar results. Data from each participant before and after treatment will be analyzed in the sweetener groups. In that way, each participant will serve as his or her own control. Post-treatment values of both treatment groups will then be compared to the control group (without treatment).

In case both sweeteners should have an effect on our endpoints, we might combine the two arms for an additional analysis comparing "no sweetener" (n= 20) vs. "sweetener" (n= 40).

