10.5 Handling of missing data and drop-outs

Missing data: as a basic principle, we will only analyse available data. In case of single missing blood values, a "last observation carried forward" (LOCF) approach will be used. Drop-outs will be replaced. Data from drop-outs will be included in the analysis if feasible (e.g. baseline values can be of value to characterize the study population).

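### No GSRS is required when a participant stops for poor tolerance, so the GSRS comparison with control can favour good tolerance, most clearly for early stops

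*Protocol*

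**What the plan says.** - **Instrument.** Protocol section 4.4 lists a single safety outcome: "Incidence and severity of gastrointestinal side effects related to the sweetener intake during the study is assessed by using a questionnaire", namely the GSRS. Section 8.2.4.1 names diarrhoea and bloating as possible adverse events and gives this as the reason for using the GSRS. Section 4.2 also makes gastrointestinal tolerance a secondary outcome.
- **Stopping.** Section 7.3 allows no change of dose: "In case the polyol is not tolerated well (gastrointestinal symptoms), the study has to be discontinued". Section 6.4 is softer and says that intolerable effects may lead to exclusion.
- **After a stop.** Section 8.2.5: "Participants who discontinue the study are not seen for a follow up visit, as the data obtained after discontinuation will not be useful". Section 7.5 plans no later visit either. No section asks for a GSRS when intake stops.
- **Timing.** Sections 4.2 and 8.2.2 and the schedule of assessments place the GSRS at baseline and in weeks 3 and 7. Section 5.1 instead says "once a week they will fill in a clinical gastrointestinal symptoms questionnaire".
- **Analysis.** Section 10.4.1: "an analysis per protocol is planned. Drop-outs will be replaced, but baseline data of drop-outs might be included to characterize the baseline population". Sections 6.4 and 7.5 keep data gathered up to the stop. Section 10.5 keeps drop-out data where feasible and gives baseline values as an example. Section 8.2.5 mentions only baseline data.
- **Adverse events.** Section 9 collects all adverse events, and section 10.4.5 lists them and compares the groups.

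**The concern.** For the metabolic endpoints, it is reasonable to say that data obtained after a stop have no use. For tolerance it is different, because the symptoms that made someone stop are the outcome itself. The people with the worst symptoms leave, may have no on-treatment score, and are replaced by people who may tolerate the sweetener.

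The control arm takes no sweetener, so it cannot lose anyone to sweetener intolerance. Any resulting bias in the comparison with control therefore has one direction, towards good tolerance. Sections 10.1 and 10.2 intend this pilot as a basis for larger studies. A tolerance result selected in this way would make the doses look easier to take than they were.

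**Working it through.** The protocol gives no drop-out rate, no expected GSRS score and no standard deviation, so there is no planned figure to reproduce. Two things can be checked: which stops leave no score, and how a missing stopper moves the arm mean.

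**1. Stop days that leave no on-treatment score** (49 treatment days, section 7.2.1)

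| Schedule | First on-treatment score | Stop days with no score | Share of days | Oldest last score at a stop |
|---|---|---|---|---|
| Weeks 3 and 7 (4.2, 8.2.2, schedule) | day 21 | 1 to 20 | 20/49 = 41% | 48 − 21 = 27 days |
| Weekly (5.1) | day 7 | 1 to 6 | 6/49 = 12% | 48 − 42 = 6 days |

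The step-up takes 2 + 3 = 5 days, so full dose starts on day 6. Under the week 3 and 7 schedule, the window without a score covers the whole step-up and days 6 to 20. That is 15 of the 49 − 5 = 44 full-dose days (34%). These are shares of calendar days, not probabilities of stopping. Under either schedule, no score is tied to the stop.

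**2. Effect of missing stoppers on an arm mean**

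Inputs: 20 per arm (section 10.2), assumed to be restored to 20 completers by replacement (section 10.4.1). Assumed: d participants stop for intolerance and contribute no score. C is the completers' mean and S is the mean the stoppers would have had.

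Mean of all starters = (20C + dS)/(20 + d)

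Shortfall of the completers' mean = d/(20 + d) × (S − C)

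The GSRS items run over seven points (section 8.2.2). The values of S − C below are assumptions: 1 gives the multiplier, 2.5 corresponds to means of 4 and 1.5, and 3.5 to means of 5 and 1.5.

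| d | d/(20 + d) | S − C = 1 | S − C = 2.5 | S − C = 3.5 |
|---|---|---|---|---|
| 1 | 1/21 | 0.05 | 0.12 | 0.17 |
| 2 | 2/22 | 0.09 | 0.23 | 0.32 |
| 4 | 4/24 | 0.17 | 0.42 | 0.58 |

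These figures apply only to stoppers whose scores are missing or left out. A stopper whose earlier score is used adds less to the shortfall, or nothing, depending on how well that score reflects the symptoms at the stop.

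**3. Are scores that do exist used?**

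Sections 6.4 and 7.5 say yes. Section 10.5 says yes if feasible. Section 10.4.1 points the other way, with a per-protocol set and only baseline data of drop-outs mentioned. Section 10.4.5 states no analysis set for safety. The question is open. An analysis plan could settle it, but could not supply a score that was never collected.

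**The case against.** The strongest reply is that intolerance is not lost. Adverse events are collected and compared by group, participants are phoned weekly (section 7.4), and they report undesired effects directly to the investigator (section 8.2.4). This stands for occurrence. It is less secure for severity, because section 9 grades causality and names no severity scale. A reader might infer that severity at the stop goes wholly unrecorded. The documents do not support that: the case report forms are not shown and may grade it, and stopping for intolerable symptoms already says something about severity.

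A second reply is that section 8.2.5 is not wrong as written. It concerns data obtained after a stop, and section 9.1.3 expects symptoms to settle at once when intake ends, so a later visit would find little. This also stands. The gap is at the stop, not after it.

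A third reply is that a score taken at the stop is taken when symptoms are at their worst. Averaging it with scheduled scores would push the sweetener arms towards poor tolerance. This is correct and shapes the fix.

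Finally, few may stop. The synopsis expects no problems at these doses, there is a step-up week, and under section 6.4 people with moderate symptoms can stay in and be scored. This limits the likely size but does not change the direction.

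**Conclusion.** The point holds in limited form. The GSRS is the named measure of gastrointestinal side effects, poor tolerance leads to a stop, and no GSRS is required at the stop. With a per-protocol analysis and replacement, the GSRS comparison with control can favour good tolerance. This is clearest for stops on days 1 to 20 under the week 3 and 7 schedule, or days 1 to 6 under the weekly one.

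Three stronger readings do not hold:

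- *Stoppers' GSRS data are certainly discarded.* Sections 6.4, 7.5 and 10.5 speak for keeping what was collected; only section 10.4.1 points clearly the other way.
- *The bias may reach a full scale point.* With d = 4 this needs every stopper at 7 and every completer at 1 (4/24 × 6 = 1.00). GSRS scales are means of several items, so this is not a realistic case.
- *Some 41% of stops go unscored.* That figure counts days, and stops need not be spread evenly over them.

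The size cannot be derived from the protocol, since both the number of stops and the score difference are assumed. The affected result is a secondary and safety outcome in an exploratory pilot; the primary glycaemic endpoint is unaffected. Priority is minor to moderate, and the change is worth making because it is cheap and the bias has one direction.

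**What to change.** - **Sections 7.5 and 8.2.5.** Require one GSRS by phone or self-report when intake stops for symptoms, completed before the substance is disclosed under section 9.1.3. Limit the statement that later data have no use to the metabolic endpoints.
- **Section 10.4.1.** Analyse gastrointestinal tolerance by assigned arm in everyone who took at least one portion, plus all controls. Keep stoppers' GSRS data even if they are replaced for the metabolic endpoints.
- **Reporting.** Give the number of stops for gastrointestinal intolerance by arm beside the GSRS result. Do not pool stop scores with the scheduled week 3 and 7 scores in the main mean. Show them separately, or use them in a worst on-treatment score or a sensitivity analysis.

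**Cost.** Wording in three sections and one 15-item form per stopper. The form is already in the study folder (section 15), interview format is allowed (section 8.2.2), and weekly phone contact exists (section 7.4). No visit or sample is added. The downside is one short call per stopper and a stop score that is not time-matched to the scheduled scores.
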